9.2.2. ESA Rescue Therapy

ESA use is not permitted during the study. The exception is a scenario in which all of the following conditions for ESA rescue therapy are met:

1. A subject has had 2 consecutive Hgb values of <8.0 g/dL more than 3 days apart.
2. The Investigator decides to treat the subject with ESA as per standard of care.
3. The Investigator deems it appropriate for the subject to continue in the study.
4. The subject continues in the study on study drug.

Any subject who is to receive or has received ESA therapy regardless of whether its use constitutes permitted ESA rescue therapy or not should be discussed with the Medical Monitor as soon as possible to decide whether the subject may remain in the study.

Subjects who received ESA during the study and who remain in the study will be excluded from the PP analysis set. Subgroup analyses will be conducted for these subjects.

Subjects who have had 2 consecutive Hgb values of <8.0 g/dL more than 3 days apart but do not meet the other criteria of ESA rescue therapy should complete the ET visit and discontinue from the study.

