15.10. Other Statistical Issues

15.10.1. Significance Levels

Unless otherwise specified, all tests will be 2 tailed using a 0.05 level of significance. All CIs will be 2-sided 95% CIs.

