### 4.3. Sample Size Considerations

#### 4.3.1. Sample Size Justifications

Because this is an open-label Phase 4 study designed to estimate within-group changes from Baseline and describe time trends of iron parameters in subgroups of subjects, it is appropriate to conduct a precision-based sample size estimation as opposed to a power-based calculation. The primary endpoint of interest is change in Hgb from Baseline at Week 24. The standard deviation

(SD) for that endpoint is estimated as 0.9 g/dL based on the Week 16 data in a prior Phase 3 study in a similar population (Keryx Study KRX-0502-306).

Assuming a population SD of 0.9 g/dL, with a sample size of 140 subjects, the 95% confidence intervals (CIs) for mean change in Hgb from Baseline to Week 24 can be estimated, allowing for a CI half-width of 0.149 g/dL.

It is assumed that 30% of the subjects in this study will drop out or be otherwise excluded from the PP population. Hence, 200 subjects will be randomized to ensure that there will be sufficient subjects at the end of the study for the longitudinal analyses (i.e., 70 evaluable subjects in each randomized treatment group). Based on prior clinical trial experience, it is estimated that half of the subjects will stay on their starting dose, and the other half will increase their dose after 12 weeks of treatment. Hence, it is expected that the 4 dosing sequence groups that will arise will have approximately equal numbers of subjects (i.e., 35 subjects are expected in each of the four dosing sequence groups (3-3, 3-6, 4-4, and 4-6 tablets/day).

The proposed sample size and the sizes of the subgroups of interest are deemed sufficient for the analyses proposed below including the longitudinal analyses.

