## **6.6. Handling of Missing Data**

### **6.6.1. Missing Efficacy Endpoints**

Subjects who discontinue will not be replaced. If efficacy endpoint data are missing, they will not be imputed.

Mixed models will be used to analyze the repeated measures data for visits up to and including Week 24 and Week 48. The Mixed Model Repeated Measures (MMRM) models described in section 8.2 implicitly adjust for missing data under the assumption of missing at random.

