## 9.6. Summary of Changes from Protocol-Specified Analyses

- The protocol states that “All subjects who are randomized and take at least 1 dose of study medication will be included in the Safety Analysis Set.” However, the Safety Analysis Set is being defined as the set of all subjects who receive at least one dose of study medication, to allow for the highly unlikely possibility that some subject (s) may receive a dose of medication prior to being randomized.
- The protocol did not discuss the potential for an ad hoc analysis. The analysis is acknowledged in this SAP and more details will be added to an amended SAP if an analysis is performed.
- The protocol did not discuss the modified Per Protocol Analysis Set. This analysis set is described in section 6.3.6 and is used for the 24-Week analysis snapshot only.
- The SAP describes analyses for the following secondary efficacy endpoints which were not included in the protocol:
  - Time from randomization to first hemoglobin increase of  $\geq$  0.5 g/dL from Baseline.
  - Change from the baseline value for each of the following:
    - eGFR
    - serum bicarbonate
    - intact parathyroid hormone
    - C-terminal fibroblast growth factor 23
    - intact fibroblast growth factor
  - Inclusion of box and scatter plots over time of the observed value and the change from Baseline for each of the iron parameter efficacy variables, TSAT and ferritin to explore the question of their stability over time on treatment.
- The protocol specified analyses of vital signs is not included in the SAP, since no related safety concerns are anticipated.

- The protocol states that all efficacy analyses will be performed based on both the FAS and the PP/mPP analysis sets, however only the PP/mPP analyses sets will be considered. Subjects are excluded from the PP/mPP analysis sets due to confounders of efficacy and thus the FAS is not appropriate for efficacy analyses. The FAS will be used for the efficacy analysis for the 'Permitted' ESA Rescue Therapy subgroup.
- The protocol did not include the baseline by visit interaction term in the efficacy model. This interaction term is included in the SAP and will be included in the model.
- Missing endpoint observations will not be imputed using a multiple imputation (MI) linear regression approach for use in an additional sensitivity analysis as specified in the protocol sections 15.7.2 and 15.10.3.

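### The SAP has no analysis that tests the primary Week 24 Hgb result against data missing not at random or against the removal of rescued subjects

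*SAP*

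**What the plan says.** **Primary analysis.** SAP 8.2 builds the Week 24 interval for each starting-dose group from an MMRM in the PP set (the modified PP set for the publication snapshot). SAP 6.6.1 leaves missing efficacy data unimputed and says the models "implicitly adjust for missing data under the assumption of missing at random".

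**Checks the protocol had.** Protocol 15.7.2 and 15.10.3 planned a regression multiple imputation (MI) with 10 datasets as the sensitivity analysis for missing data. Protocol 15.7 planned every efficacy analysis in the FAS as well, to show the effect of subject exclusions.

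**What SAP 9.6 does.** It removes both. On the MI it says "Missing endpoint observations will not be imputed using a multiple imputation (MI) linear regression approach" and gives no reason. It drops the FAS on the ground that excluded subjects carry confounders of efficacy, and keeps it only for the subgroup given permitted ESA rescue.

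**Who leaves the study.**
- Anyone who stops study drug, with lack of efficacy a listed reason (Protocol 8.3.1).
- Anyone given IV iron or a transfusion (Protocol 9.2.1).
- Subjects with two consecutive Hgb values below 8.0 g/dL, more than 3 days apart, who "do not meet the other criteria of ESA rescue therapy should complete the ET visit and discontinue from the study" (Protocol 9.2.2).

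**Who leaves the PP set.** SAP 6.3.5 excludes anyone given ESA (permitted or not), IV iron or a red cell transfusion at any time during the study.

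**What remains.** SAP 8.3 keeps an ANCOVA of Hgb change in PP subjects who complete the Week 24 or Week 48 visit.

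**The concern.** Two separate problems go unexamined.

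(a) **Missing data.** A subject who stops drug has no Hgb after the Early Termination (ET) visit. The MMRM fills the gap from the subject's own earlier values and from subjects who stayed. Low values seen before or at ET do count, so the worry is only the further departure that those values do not predict. The trial data cannot test for it, because nothing is measured afterwards.

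(b) **Selection.** A subject given ESA, IV iron or transfusion is deleted from the PP set outright, pre-rescue Hgb included. Because the exclusion applies at any time in the study, a rescue at Week 40 also deletes that subject's valid Week 24 value. The MMRM makes no prediction for such subjects, so MAR is not the relevant assumption. The FAS analysis was the check.

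The stake is the headline estimate. The study estimates change within each group, with no untreated arm in which a similar error might cancel. If the subjects who leave or are rescued do worse than those kept, the reported mean is too high and no planned table would show it.

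**Working it through.** **Step 1. Reproduce the plan's precision.** SAP 4.3.1 says "it is appropriate to conduct a precision-based sample size estimation as opposed to a power-based calculation". Its inputs are "Assuming a population SD of 0.9 g/dL, with a sample size of 140 subjects", "allowing for a CI half-width of 0.149 g/dL". Protocol 15.10.1 sets "All CIs will be 2-sided 95% CIs".

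Half-width = 1.96 × 0.9 / √140 = 0.1491 g/dL (0.1504 with the t quantile), which agrees with 0.149. Randomized number = 140 / (1 − 0.30) = 200, which also agrees. For one arm with 70 evaluable subjects: 1.96 × 0.9 / √70 = 0.211 g/dL.

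**Step 2. Shift in the mean.** Let f be the share of subjects affected and delta their average shortfall in g/dL. For (a), f is the share without a Week 24 value and delta is measured against the MAR prediction. For (b), f is the share deleted for rescue and delta is measured against the subjects kept. In each case

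shift = f × delta, and the delta that shifts the mean by one half-width = half-width / f.

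The only related figure in the plan is in SAP 4.3.1: "It is assumed that 30% of the subjects in this study will drop out or be otherwise excluded from the PP population". It combines dropout with PP exclusion and refers to the whole study, so f at Week 24 is an assumption, shown here from 10% to 30%.

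| Assumed f | Shift at delta 0.5 | Shift at delta 1.0 | Delta for pooled 0.149 | Delta for one arm 0.211 |
|---|---|---|---|---|
| 30% | 0.15 | 0.30 | 0.50 | 0.70 |
| 20% | 0.10 | 0.20 | 0.75 | 1.05 |
| 10% | 0.05 | 0.10 | 1.49 | 2.11 |

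**Step 3. Would any MAR method or the completers analysis show it?** A simulation used 400 replicates, 200 subjects, 7 visits, SD 0.9, mean change rising from 0.1 to 0.7 g/dL, dropout depending on the previous value (about 32% missing at the last visit) and 10 imputations. Delta was then added to values after dropout. The likelihood method was sequential regression, which is equivalent to the MMRM under monotone dropout. Mean change at the last visit, in g/dL:

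| Delta | Truth | MMRM-type likelihood | Regression MI | Completers |
|---|---|---|---|---|
| 0 | 0.693 | 0.695 | 0.696 | 0.771 |
| −0.5 | 0.542 | 0.701 | 0.702 | 0.777 |
| −1.0 | 0.375 | 0.697 | 0.696 | 0.777 |

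MMRM and MI agree throughout, and both stay near 0.70 as the truth falls. The gap at delta −0.5 is 0.701 − 0.542 = 0.159, close to 0.315 × 0.5 = 0.158 from Step 2. Completers are too high even under MAR.

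**Step 4. How far must the delta grid reach?** The lower limit reaches 0 when delta = (mean − half-width) / f. With an assumed mean change of 0.5 to 0.8 g/dL, f = 30% and the half-width held at 0.15, this runs from (0.5 − 0.15)/0.30 = 1.17 to (0.8 − 0.15)/0.30 = 2.17 g/dL. A grid that stops at 1.0 could miss the tipping point.

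**The case against.** The best defense has four parts.

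**The MI was never a test.** A reader might infer that dropping it is what made the result depend on MAR. The documents do not support that: a regression MI without a delta also assumes MAR, and Step 3 shows the two agreeing. SAP 9.6 also discloses the removal. This stands in full. The gap is the lack of any analysis outside MAR.

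**Falling Hgb does not force exit.** A reader might infer that it does. Exit on Hgb requires two values below 8.0 g/dL and failure to meet the ESA rescue conditions. Week 12 subjects who miss the response criteria are up-titrated, and rescued subjects may stay. An ET value inside a visit window enters the MMRM (note c to SAP Table 2). Withdrawal driven by observed Hgb is what MAR covers. This stands and narrows problem (a) to departures beyond the observed values.

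**30% is too high for Week 24.** It includes PP exclusions, covers 48 weeks, and is already netted out of the 140. This stands, hence the 10% to 30% range. At 10% the required delta is large.

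**Other looks remain.** The completers ANCOVA rests on a stronger assumption than MAR and, like the MMRM, uses the PP set, so it tests neither problem. The permitted-ESA subgroup is reported apart from the primary estimate, with descriptive statistics only if it has 3 to 29 subjects. This part fails.

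The sponsor's reason for dropping the FAS, confounding by rescue, is fair for values after rescue. It does not justify deleting values before it.

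**Conclusion.** The point holds as a weakness of a disclosed plan; the documents do not contradict each other here. Nothing in the SAP would show whether the primary Week 24 estimate is sensitive to subjects leaving for reasons their Hgb did not predict, or to the deletion of rescued subjects.

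The size rests on two unknowns, f and delta. A shortfall of 0.50 g/dL matches the pooled half-width only at f = 30%. At 20% it takes 0.75 and at 10% it takes 1.49; for one arm, the level at which SAP 8.2 states the primary interval, the figures are 0.70, 1.05 and 2.11.

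The upward direction is a reasonable expectation. Permitted ESA rescue requires Hgb below 8.0 g/dL, while entry required at least 8.5 at screening. For IV iron and transfusion the protocol sets no Hgb threshold, so the direction there is inferred.

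A reader might conclude that a positive change would be overturned. The documents do not support that: under the assumptions of Step 4 it takes a delta of 1.17 to 2.17 g/dL. What is at risk is the size of the reported change and confidence in its precision.

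**What to change.** Amend SAP 6.6.1, 8.2 and 9.6 to add one sensitivity analysis of Hgb change at Weeks 24 and 48 in the FAS:

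- Keep all values before rescue. Set values after ESA, IV iron or transfusion to missing. This meets the confounding objection in SAP 9.6 without discarding valid data.
- Use delta-adjusted MI. Apply delta to every value missing because of discontinuation or rescue, including rescued subjects who stay in the study; otherwise they would be imputed under plain MAR.
- Start at delta = 0, which shows the effect of the PP exclusions alone under MAR, and go down in steps of 0.25 g/dL until the lower 95% limit reaches 0.
- Report the estimate and interval at each delta, by starting-dose group and overall.

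The cost is one SAP paragraph and one extra program, with no change to conduct, dosing or data collection. The downside is that the sensitivity estimate may be less favorable than the primary one.

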## 11. APPENDIX

### **11.1. Work Productivity and Activity Impairment (WPAI) Questionnaire Specific Health Problem V2.0 (WPAI:SHP)\***

The following questions ask about the effect of your Anemia associated with Chronic Kidney Disease on your ability to work and perform regular activities. *Please fill in the blanks or circle a number, as indicated.*

1. Are you currently employed (working for pay)? **NO** **YES**  
*If NO, check "NO" and skip to question 6.*

The next questions are about the **past seven days**, not including today.

2. During the past seven days, how many hours did you miss from work because of problems associated with your Anemia associated with Chronic Kidney Disease? *Include hours you missed on sick days, times you went in late, left early, etc., because of your Anemia associated with Chronic Kidney Disease. Do not include time you missed to participate in this study.*

## HOURS

3. During the past seven days, how many hours did you miss from work because of any other reason, such as vacation, holidays, time off to participate in this study?

Document: \\quintiles.net\enterprise\apps\sasdata\sasb\sas\Keryx\KRX-0502\Biostatistics\Documentation\SAP\

Author:

Version Number:

1.1

HOURS

4. During the past seven days, how many hours did you actually work?

HOURS (If "0", skip to question 6.)

5. During the past seven days, how much did your Anemia associated with Chronic Kidney Disease affect your productivity while you were working?

*Think about days you were limited in the amount or kind of work you could do, days you accomplished less than you would like, or days you could not do your work as carefully as usual. If Anemia associated with Chronic Kidney Disease affected your work only a little, choose a low number. Choose a high number if Anemia associated with Chronic Kidney Disease affected your work a great deal*

Consider only how much Anemia associated with Chronic Kidney Disease affected productivity while you were working

Anemia associated with Chronic Kidney Disease had no effect on my work	0 1 2 3 4 5 6 7 8 9 10	Anemia associated with Chronic Kidney Disease completely prevented me from working
--	------------------------	--

CIRCLE A NUMBER

6. During the past seven days, how much did your Anemia associated with Chronic Kidney Disease affect your ability to do your regular daily activities, other than work at a job?

*By regular activities, we mean the usual activities you do, such as work around the house, shopping, childcare, exercising, studying, etc. Think about times you were limited in the*

*amount or kind of activities you could do and times you accomplished less than you would like. If Anemia associated with Chronic Kidney Disease affected your activities only a little, choose a low number. Choose a high number if Anemia associated with Chronic Kidney Disease affected your activities a great deal.*

Consider only how much anemia associated with chronic kidney disease affected your ability to do your regular daily activities, other than work at a job

Anemia associated with Chronic Kidney Disease had no effect on my daily activities	0    1    2    3    4    5    6    7    8    9    10	Anemia associated with Chronic Kidney Disease completely prevented me from doing my daily activities
--	--	--

**CIRCLE A NUMBER**

**11.2. WPAI:SHP QuestionnaireV2.0**

The instructions given by **REILLY ASSOCIATES Health Outcomes Research** at [http://www.reillyassociates.net/WPAI\\_Scoring.html](http://www.reillyassociates.net/WPAI_Scoring.html) and inserted below will be used to score the WPAI:SHP questionnaires completed by each subject. Questions 1, 2, 3, 4, 5, and 6 in those instructions correspond to the questions with the same number in the questionnaire given above that subjects will complete during this study.

WPAI outcomes are expressed as impairment percentages, with higher numbers indicating greater impairment and less productivity, i.e., worse outcomes, as follows:

**Questions:**

Document: \\quintiles.net\enterprise\apps\sasdata\sasb\sas\Keryx\KRX-0502\Biostatistics\Documentation\SAP\

- 1 = currently employed
- 2 = hours missed due to specified problem
- 3 = hours missed other reasons
- 4 = hours actually worked
- 5 = degree problem affected productivity while working
- 6 = degree problem affected regular activities

*Scores:*

Multiply scores by 100 to express in percentages.

Percent work time missed due to problem:  $Q2/(Q2+Q4)$

Percent impairment while working due to problem:  $Q5/10$

Percent overall work impairment due to problem:  $Q2/(Q2+Q4)+[(1-(Q2/(Q2+Q4)))\times(Q5/10)]$

Percent activity impairment due to problem:  $Q6/10$

### 11.3. Functional Assessment of Chronic Illness Therapy (FACIT) Fatigue Scale (Version 4)

Below is a list of statements that other people with your illness have said are important. Please circle or mark one number per line to indicate your response as it applies to the past 7 days.

		Not at all	A little bit	Some- what	Quite a bit	Very much
H17	I feel fatigued.....	0	1	2	3	4
H12	I feel weak all over .....	0	1	2	3	4
An1	I feel listless ("washed out").....	0	1	2	3	4
An2	I feel tired .....	0	1	2	3	4
An3	I have trouble starting things because I am tired.....	0	1	2	3	4
An4	I have trouble finishing things because I am tired.....	0	1	2	3	4
An5	I have energy .....	0	1	2	3	4
An7	I am able to do my usual activities .....	0	1	2	3	4
An8	I need to sleep during the day.....	0	1	2	3	4
An12	I am too tired to eat.....	0	1	2	3	4
An14	I need help doing my usual activities .....	0	1	2	3	4
An15	I am frustrated by being too tired to do the things I want to do	0	1	2	3	4
An16	I have to limit my social activity because I am tired.....	0	1	2	3	4

English (Universal)  
Copyright 1987, 1997

16 November 2007 Page 1 of 1

## 11.4. FACIT-Fatigue Subscale Scoring

The instructions for the FACIT-Fatigue Subscale Scoring Guidelines (Version 4) below were copied from the link to **FACIT-Fatigue: Functional Assessment of Chronic Illness Therapy-Fatigue**; a 13-item FACIT Fatigue Scale Scoring and Interpretation found at <http://www.facit.org/FACITOrg/Questionnaires>. These instructions for scoring will be used as described below and if less than 7 of the 13 FACIT Fatigue Subscale items are missing the Total Score will be missing.

Instructions:\*

1. Record answers in "item response" column. If missing, mark with an X
2. Perform reversals as indicated, and sum individual items to obtain a score.
3. Multiply the sum of the item scores by the number of items in the subscale, then divide by the number of items answered. This produces the subscale score.

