$$\text{BMI (kg/m}^2\text{)} = [\text{Weight (kg)}] / [\text{height (m)}]^2.$$

Since height and weight are recorded in inches and pounds, respectively, note that

$$\text{Weight (kg)} = \text{Weight (lb)} / 2.2046$$

$$\text{Height (m)} = 0.0254 * \text{height (in)}.$$

Round weight and height to one decimal place before calculating BMI and round BMI to one decimal place.

Descriptive statistics of the following CKD characteristics will be presented in a table separate from the other characteristics:

- Age (years) at CKD Diagnosis
- CKD Primary Cause
- Baseline CKD Stage

Age at CKD Diagnosis is the CKD initial diagnosis age derived using the expression in section 6.5.1.

Other baseline characteristics include:

- Work Productivity and Activity Impairment Scores (See section 11.2 for scoring instructions.)

- Percent work time missed due to anemia associated with CKD
- Percent impairment while working due to anemia associated with CKD
- Percent overall work impairment due to anemia associated with CKD
- Percent activity impairment due to anemia associated with CKD
- FACIT-Fatigue Subscale Score (See section 11.4 for scoring instructions.)
- Number of hospitalizations
- Duration of hospitalization stay (days)
- The baseline evaluation for the following parameters reported by the central laboratory:
  - Hemoglobin (Hgb)
  - Estimated glomerular filtration rate (eGFR)
  - eGFR category: <30, 30 - 44, and >=45 ml/min/1.73m^2
  - Transferrin saturation (TSAT)
  - Ferritin
  - Phosphorus, i.e., serum phosphate
  - Intact parathyroid hormone (iPTH)
  - Intact Fibroblast growth factor 23 (iFGF23)
  - C-terminal Fibroblast growth factor 23 (cFGF23)
  - Spot urine protein-to-creatinine ratio

Descriptive statistics of the laboratory parameters will be displayed in conventional units.

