Intact parathyroid hormone (iPTH), C-terminal fibroblast growth factor 23 and intact fibroblast growth factor 23 are only measured at Randomization Day, Week 24 and Week 48. Therefore, the type of ANCOVA model as described above for change for Baseline Hgb in the PP/mPP analysis subjects who complete the Week 24 visit and those who complete the Week 48 visit will be used to obtain the 95% confidence intervals for the means of the following:

1. Change in intact parathyroid hormone (iPTH) from Baseline to Weeks 24 and 48
2. Change in C-terminal fibroblast growth factor 23 from Baseline to Weeks 24 and 48
3. Change in intact fibroblast growth factor 23 from Baseline to Weeks 24 and 48.

Box plots over time of the observed value and the change from Baseline for each of the efficacy parameters, Hgb, TSAT, ferritin and serum phosphate will be provided. The box plots will be constructed based on observations made during the window of time designated for each visit given in section 6.5.4. If there are visits that are out of window, a scatter plot of the in-window and out of window observations will be used along with the box plots to explore the question of the stability of Hgb, TSAT, ferritin and serum phosphate during treatment with the study medication.

The Kaplan-Meier estimator of the survival function of time from randomization to first increase from Baseline Hgb of at least 0.5 g/dL for each of the two starting dose treatment groups will be obtained. The Kaplan-Meier plot of the functions for the two starting doses will be presented on a single figure.

A table will be presented that shows for the PP/mPP analysis set by treatment group the following for the event, time from randomization to first increase from Baseline Hgb of at least 0.5 g/dL, during the Dose Titration Period:

- Estimated median time in days;
- Number and percentage of subjects who had at least one event;

- Number and percentage of subjects with time to the event censored (Censoring occurs if a subject does not have the event prior to either completing the Week 24 visit or discontinuing from the study prior to the Week 24 visit.).

Tables displaying descriptive statistics will be provided for the Week 24 analysis and the Final analysis for the following secondary efficacy endpoints:

- Change in FACIT Fatigue Scale from Baseline at Weeks 24 and 48;
- Change in WPAI questionnaire specific health problem score from Baseline at Weeks 24 and 48

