**4. The higher the score, the better the QOL.**

Subscale	Item Code	Reverse item?	Item response	Item Score
FATIGUE	HI7	4 -	_____	= _____
	HI12	4 -	_____	= _____
SUBSCALE	An1	4 -	_____	= _____
	An2	4 -	_____	= _____
Score range: 0-52	An3	4 -	_____	= _____
	An4	4 -	_____	= _____
Score range: 0-52	An5	0 +	_____	= _____
	An7	0 +	_____	= _____
	An8	4 -	_____	= _____
	An12	4 -	_____	= _____
	An14	4 -	_____	= _____
	An15	4 -	_____	= _____
	An16	4 -	_____	= _____
Sum individual item scores: _____				
Multiply by 13: _____				
Divide by number of items answered: _____ =Fatigue Subscale score				

\*See the instructions related to missing data in FACIT subscales within the FACIT Administration and Scoring Guidelines on the FACIT.org website.

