**11.4.1. Handling Missing Items on FACIT Fatigue Subscale**

Negatively stated items are reversed by subtracting the response from “4”. After reversing proper items, all subscale items are summed to a total, which is the subscale score. For all FACIT scales and symptom indices, the higher the score the better the QOL.

If there are missing items, subscale scores can be prorated. This is done by multiplying the sum of the subscale by the number of items in the subscale, then dividing by the number of items actually answered. This can be done by using the formula below:

Prorated subscale score = [Sum of item scores] x [N of items in subscale] ÷ [N of items answered]

When there are missing data, prorating by subscale in this way is acceptable as long as more than 50% of the items were answered (i.e, more than 7 of the 13 FACIT Fatigue Subscale items).

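### The FACIT-Fatigue missing-item rule in SAP 11.4 is reversed, and SAP 11.4.1 contradicts both it and itself at exactly 7 answered items

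*SAP*

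**What the plan says.** SAP section 11.4 adopts scoring instructions described as "a 13-item FACIT Fatigue Scale Scoring and Interpretation". Its step 3 multiplies the sum of the item scores by the number of items in the subscale and divides by the number answered. The same section adds a rule for incomplete forms: "if less than 7 of the 13 FACIT Fatigue Subscale items are missing the Total Score will be missing".

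Section 11.4.1 repeats the proration formula and sets its own condition: "prorating by subscale in this way is acceptable as long as more than 50% of the items were answered". A parenthesis turns the percentage into a count: "more than 7 of the 13 FACIT Fatigue Subscale items".

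A footnote to the scoring form in 11.4 adds a pointer to an outside source: "See the instructions related to missing data in FACIT subscales within the FACIT Administration and Scoring Guidelines". The SAP does not say which of these governs if they differ. Protocol Appendix B shows the questionnaire but has no rule for unanswered items.

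The score is used in two places. In section 7.3 it is a baseline characteristic: "FACIT-Fatigue Subscale Score (See section 11.4 for scoring instructions". In section 8.3 it is a secondary efficacy endpoint, given as "Change in FACIT Fatigue Scale from Baseline at Weeks 24 and 48". It is item 12 in the secondary endpoint list of section 3.2.2, and Table 3 in section 8.1 assigns it a descriptive analysis.

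**The concern.** A missing-item rule should withhold a score when too few items were answered. The sentence in 11.4 withholds it when too few items are *missing*, which is the reverse. It discards complete and nearly complete forms and places no bar on sparse ones. Section 11.4.1 has the direction right, but its percentage and its count do not describe the same threshold.

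The threshold decides who contributes to the endpoint. Under SAP 6.6.1 missing efficacy data are not imputed, and under 6.5.3 a change from baseline is missing if either value is missing. A single baseline form with exactly 7 answers, scored or not, therefore decides whether that subject can have a change at Week 24 and at Week 48. Both codings would give plausible tables, so nothing in the output would show that a choice had been made.

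**Working it through.** **Inputs.** The scale has 13 items and a score range of 0–52 (SAP 11.4). Write *a* for items answered and *m* = 13 − *a* for items missing. The rules are:

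- 11.4 as printed: score withheld if *m* < 7. Otherwise step 3 gives sum × 13 / *a*, which needs *a* > 0.
- 11.4.1, percentage clause: score allowed if *a*/13 > 0.5.
- 11.4.1, count clause: score allowed if *a* > 7.

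**The SAP's own conversion of 50% to a count.** 50% of 13 is 6.5, so the smallest whole number above it is 7. Check: 6/13 = 46.2% and 7/13 = 53.8%. The percentage clause means at least 7 answered. The SAP's count, more than 7, means at least 8 (8/13 = 61.5%). The conversion does not reproduce.

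**All 14 possible counts under each rule.**

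| Answered | Missing | 11.4 as printed | 11.4.1, percentage | 11.4.1, count |
|---|---|---|---|---|
| 0 | 13 | no score possible (division by zero) | no score | no score |
| 1–6 | 12–7 | score | no score | no score |
| 7 | 6 | no score | score | no score |
| 8–13 | 5–0 | no score | score | score |

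**Disagreements.**

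- 11.4 against the percentage clause: 6 counts (1–6 answered) + 7 counts (7–13 answered) = 13 of 14. They agree only on the blank form.
- 11.4 against the count clause: 6 counts (1–6 answered) + 6 counts (8–13 answered) = 12 of 14. They agree at 7 answered and on the blank form.
- 11.4 and 11.4.1 both satisfied: 0 of 14, whichever clause of 11.4.1 is used.
- The two clauses of 11.4.1 against each other: 1 of 14, at exactly 7 answered.

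These tallies treat the blank form as unscored under 11.4 because no score can be computed. If one counts only whether 11.4 *withholds* the score, the blank form becomes a further disagreement and the first two figures are 14 and 13.

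**What the printed rule would let through.** With one item answered and its item score equal to 4, step 3 gives 4 × 13 / 1 = 52, the top of the scale. The printed sentence does not stop this, yet it would remove a form with all 13 items answered.

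**The proposed correction.** With the score missing when *a* < 7, forms with 7–13 answers are scored and forms with 0–6 are not. This matches the percentage clause at all 14 counts. It differs from the present count clause at one (*a* = 7), and changing that gloss to at least 7 removes the difference.

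**The case against.** The strongest reply is that the sentence in 11.4 is an evident slip, with *missing* written for *answered*, and that nobody would program it literally. Step 3 and the scoring form both divide by the number answered, 11.4.1 states the direction correctly, and the footnote points to the instrument's own guideline. Section 7.3 sends the reader to 11.4, which can be taken to include 11.4.1. A literal run would give an empty table, and version 1.1 of the SAP followed sponsor comments on dry-run outputs, although the document does not say whether those covered this scale. On that view only the form with exactly 7 answers remains open, on a secondary endpoint for which no test or model is planned.

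Much of this stands. The slip is the likely explanation, the literal outcome would probably be caught, and the practical residue is the 7-answer boundary. The list in SAP 9.6 covers departures from the protocol, which has no missing-item rule, so its silence proves nothing. The tally over 14 counts describes the rules and not how many subjects are affected.

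It does not remove the need for a correction. A program that does the sensible thing departs from the written SAP without record, and an independent programmer working from the text could not reproduce it with certainty. Correcting the slip in 11.4 also leaves the two clauses of 11.4.1 in conflict.

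**Conclusion.** The concern holds. As printed, 11.4 withholds the score from every form with 7 to 13 answers. Section 11.4.1 contradicts it, and its own two clauses differ at exactly 7 answers. Applied together, the two sections score no form.

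The consequence is limited. The FACIT-Fatigue endpoint is descriptive, the only other use found is the baseline summary, and the primary hemoglobin analysis and the sample size do not depend on it. The documents do not say how often forms with exactly 7 answers occur, so the effect on any reported mean cannot be sized.

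Two points are inference. The intended direction of 11.4 is read from 11.4.1 and the proration formula. The cut-off of at least 7 is what the more-than-50% clause implies for 13 items. The outside scoring guideline that the SAP cites was not available for checking.

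**What to change.** 1. In SAP 11.4, state that the total score is missing if fewer than 7 of the 13 items are **answered**.
2. In SAP 11.4.1, change the parenthetical count to **at least 7** of the 13 items, so that it agrees with the percentage beside it. The sponsor should confirm this cut-off against the guideline cited in the footnote.
3. Before database lock, check the scoring program against the corrected text, including test forms with 0, 6, 7, 8 and 13 answers.

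The cost is two wording corrections and one program check. No new data are needed and no other analysis changes.
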